Principal Investigator: [name]

Study Number: 17-00051

NCT Number: NCT03183778

1) **Protocol Title**

Use of patiomer to transition chronic kidney disease patients with hyperkalemia to a plant-rich diet

2) **Objectives**

The purpose of this proof-of-concept controlled-feeding study is to determine whether patiomer (Veltassa®, Relypsa, Inc., Redwood City, CA) can be used to maintain normal serum potassium concentrations in chronic kidney disease (CKD) patients who are transitioned to a plant-rich diet. We hypothesize that patiomer can be titrated to maintain serum potassium concentrations in the normal range, allowing CKD patients to consume a plant-rich diet without developing hyperkalemia. If successful, we plan to conduct a randomized clinical trial to determine the quality of life and health outcomes of CKD patients with hyperkalemia undergoing an intensive behavioral intervention to promote a low-potassium diet, or a plant-rich diet plus patiomer.

3) **Background**

An estimated 22.5% of adults 60 years and older in the U.S. have stages 3-5 CKD¹. Individuals with stages 3-5 CKD are at increased risk of high blood potassium concentrations (hyperkalemia), which in severe cases can disrupt the normal contractility of the heart². Several factors are thought to contribute to hyperkalemia in CKD patients, in particular diabetes, dietary potassium intake, and medications that inhibit the renin-angiotensin-aldosterone system (RAAS inhibitors, which include angiotensin converting enzyme inhibitors and angiotensin 2 receptor blockers; ACEi and ARBs)^{3,4}. Given the potential health consequences of hyperkalemia, stages 3-5 CKD patients, even those without hyperkalemia, are often directed to follow a low-potassium diet⁴.

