Unfortunately, following a low-potassium diet involves limiting or avoiding many plant-based sources of potassium, including nuts, seeds, legumes, and high-potassium fruits and vegetables. With accompanying dietary restriction requirements for sodium, phosphate and protein, the diet can be burdensome and unpalatable for the patients, and can make it difficult to obtain essential nutrients⁴. In addition to providing potassium, high-potassium plant foods are important sources of dietary fiber, organic anions (potential base), antioxidants and other phytochemicals (e.g., phytosterols), and therefore, a low-potassium diet may contribute to hypertension (low potassium), constipation and diarrhea (low fiber), dysglycemia and dyslipidemia (low fiber and other phytochemicals), metabolic acidosis (low organic anions), oxidative stress and inflammation (low antioxidants and other phytochemicals)⁴.

Patiomer is approved by the U.S. Food and Drug Administration (FDA) for the treatment of hyperkalemia, and has been demonstrated to be effective in treating hyperkalemia in CKD patients⁵. However, the potential of this new therapy for allowing CKD patients to liberalize their diets, and the potential health benefits of following a plant-rich diet in advanced CKD are yet unexplored.

4) **Inclusion and Exclusion Criteria**

The focus of the study is to: a) evaluate the efficacy of patiomer for managing serum potassium concentrations in CKD patients as they are transitioned to a plant-rich diet that includes high-potassium fruits and vegetables, and b) evaluate the impact of a plant-rich diet on health outcomes in CKD patients. We will recruit 10 CKD patients with persistently elevated serum potassium concentrations in New York City.

i. Inclusion criteria. In order to be eligible for the study, the individual must meet the following criteria:

a) 19-80 years of age

b) Stages 3-4 CKD (estimated glomerular filtration rate (eGFR) of 15-59 mL/min/1.73m², not

treated with dialysis)

c) No prior treatment with patiromer

d) Mild hyperkalemia (potassium 5.1 to <6.5 mEq/L) on one of the last two blood tests

e) No prior episodes of moderate-severe hyperkalemia (potassium \geq 6.5 mEq/L) in the past 6 months

f) Deemed appropriate for the intervention by the patient’s nephrologist, considering the patient’s prognosis, cognition and pending treatments (e.g., dialysis)

ii. Exclusion criteria. We will exclude from participation patients with the following characteristics:

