8) Study endpoints

Among 10 stages 3-4 CKD patients with persistent, mild hyperkalemia, we will evaluate, in a quasi-experimental, controlled feeding study, the efficacy of patiomer for maintaining normal serum potassium concentrations when following a plant-rich diet that includes high-potassium fruits and vegetables, as well as the effects of this diet on health outcomes. The participants will be transitioned gradually to a plant-rich diet, as outlined further below.

The interventions will be evaluated primarily in terms of serum potassium concentrations, but health outcomes will also be assessed, including blood pressure, gastrointestinal symptoms, and fasting concentrations of phosphorus, calcium, magnesium, albumin, glucose, insulin, cholesterol, LDL-cholesterol, HDL-cholesterol, triglycerides, urea nitrogen, bicarbonate and C-reactive protein. For all parameters, baseline values will be compared to values at the end of each diet phase (weeks 2 and 4).

9) **Procedures involved**

a. Design.

We will conduct an unblinded, quasi-experimental, controlled feeding study, which will be coordinated through the New York University – Health and Hospitals Corporation Clinical and Translational Science Institute (CTSI). Throughout the study, participants will be prescribed patiromer by the study nephrologist ([name]), which will be administered through the CTSI pharmacy. After a 1-week stabilization period, in which participants are prescribed Patiromer while following their usual diets, the feeding component of the study will occur in two phases. During the first phase (week 2), participants will be transitioned to a plant-rich renal diet, which contains moderate protein (10-15% of kcal), restricts dairy products (≤ 1 serving/day), and eliminates high-potassium fruits and vegetables. During the second phase (weeks 3 and 4), the diet will be altered to provide at-least half of fruits and vegetables from high-potassium sources. To reduce participant burden, meals will be delivered to participants by Portable Chef (New York, NY) three times per week.

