Table 4. Summary of study visits and procedures

	Screening	Baseline	Wk 1	Wk 2	Wk 3	Wk 4
Baseline Questionnaire (comorbidities, sociodemographics, tobacco and alcohol use, use of dietary supplements and urine output)		X				
Medical Chart Review (cause of CKD, comorbidities, urine albumin concentration)		X				
Medical Chart Review (medications)		X		X		X
Dietary Assessment (3-day food record)			X			
Anthropometrics (height)	X					
Anthropometrics (weight)	X			X		X
Fasting Blood Test (potassium)	X		X	X	X	X
Fasting Blood Test (phosphorus, calcium, magnesium, albumin, glucose, insulin, cholesterol, LDL-cholesterol, HDL-cholesterol, triglycerides, urea nitrogen, bicarbonate and C-reactive protein)		X		X		X
Blood Pressure (systolic and diastolic blood pressure)		X		X		X
Gastrointestinal Symptoms Questionnaire (frequency and severity of abdominal cramping, abdominal discomfort, indigestion, infrequent or difficult to pass bowel movements, flatulence, loose or watery stools in previous week)		X	X	X		X

10) Data and Specimen Banking

No samples will be stored for future analyses in this study.

11) Data Management

Information to be obtained from participants includes height and weight, blood pressure, medical history, blood tests, and self-administered questionnaires (sociodemographics, clinical and comorbid conditions/ management, cigarette and alcohol use and gastrointestinal symptoms). None of the data to be collected is considered sensitive in nature. Some of the participant data such as laboratory results will be linked to the participant's name. Other data (e.g., height, weight, blood pressure, medical history, and surveys) will be linked to the participant through a subject ID number. As a further measure to protect participants' privacy, different subject ID numbers will be used for study measurements and for coordinating the feeding component of the study. We will maintain separate files for identified and de-identified data in locked file cabinets in a locked office. Access to these data will be restricted to the PI ([name]), and study staff responsible for gathering data and maintaining research files. Data will be entered into a centralized database maintained on a secure server. Data

in these files will be linked to participants only through their ID number – this file will be maintained in a locked filing cabinet at [name]. All data collected will be used expressly for the purpose of the proposed study.

a. Overview.

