A descriptive analysis of all data collected will be performed using appropriate graphical and numerical exploratory data techniques. The information obtained from this preliminary investigation of the data will be used to: (1) assess data quality and completeness, (2) describe univariate distributions at baseline and follow up, and (3) create summary statistical data for outcome variables at each time point, including the proportion of participants with hyperkalemia. We will identify features of the data that may necessitate special analytic methods (e.g., excess zeros, missing data, departures from distributional assumptions, outliers).

For analytic analyses, we will examine: (1) changes in outcome variables (blood pressure, gastrointestinal symptoms, and fasting concentrations of potassium, phosphorus, calcium, magnesium, albumin, glucose, insulin, cholesterol, LDL-cholesterol, HDL-cholesterol, triglycerides, urea nitrogen, bicarbonate and C-reactive protein), and covariates (weight, medications, dose of Patiromer) between baseline and the end of each diet phase, and (2) relationships between the changes in outcome variables and covariates. Changes in study outcomes will be graphically depicted using means \pm SD or median (IQR) as measures of central tendency and variance. Changes in study outcomes will be analyzed using repeated-measures analysis of variance with post-hoc Tukey HSD test. Because of the small sample size, covariates will be reported instead of being included in a multivariable model. Depending on the types of covariate and outcome of interest, subgroup analyses may be performed with these participants removed from the dataset. For example, if a participant's dose of phosphorus binder medications changed during the study, the analysis of phosphorus concentrations would be conducted with/without this participant. Given the short duration of this study (4 weeks) in relation to typical monitoring of patients with stage 3B-4 CKD, we expect that that few, if any, subgroup analyses will be required.

12) Provisions to Monitor the Data to Ensure the Safety of Subjects

Protection against Risk.

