This study will not provide the investigators with data to demonstrate improvements in health-related quality of life, morbidity, mortality, and utilization or cost of care. However, if proven efficacious, future CKD patients may benefit from the knowledge generated from this study regarding the need to limit or avoid high-potassium plant foods, and the potential health benefits of a plant-rich dietary pattern. Because this is a

proof-of-concept study, the emphasis has been placed on safety and internal validity rather than real-world applicability and generalizability to the CKD population. Consequently, this is just a first step in several needed to benefit future CKD patients. Additional longer-term studies in free-living CKD patients would be needed before any such changes in practice could be realized.

16) Vulnerable populations

No vulnerable populations are included in this study.

17) Multi-site research

Not applicable.

18) Community-based participatory research

Not applicable.

19) Sharing results with subjects

The study results will not be shared with participants who will be expected to return to usual care practices upon completion of the study.

20). Setting

Research activities will occur at the CTSI CRC and Renal Clinic of the New York VA. Ethical review will be obtained from the Institutional Review Board at NYULMC.

21) Resources available

i). Personnel.

INVESTIGATORS

[name] (Principal Investigator, Effort = 0.6 CM) is a Professor in the Departments of Medicine and Neuroscience and Physiology at the New York University School of Medicine, and Chief of Nephrology at the Renal Clinic of the New York VA. He is a nephrologist with extensive clinical and research experience with individuals with chronic kidney disease, including trials of medications. He is well-known in the local nephrology community. [name] is co-investigator to [name] ongoing Diabetes Healthy Hearts study (R01), and pending Kidneys and Behavioral Management of Phosphorus study (R21). He will provide crucial medical oversight to the study, in particular safety monitoring, patiomer prescriptions, and assist with interpretation of data from a medical perspective in the dissemination of study results. [name] has a part-time university position and his effort is estimated as a function of his university appointment.

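### For blood pressure and the biochemistry panel, every planned change from baseline combines the start of patiromer with the change of diet, yet the aim is worded as the effect of the diet

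*Combined protocol and SAP*

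**What the plan says.** - **Sequence (section 9.a).** Patiromer is prescribed throughout. The order is: "After a 1-week stabilization period, in which participants are prescribed Patiromer while following their usual diets", then the low-potassium plant-rich diet in week 2, then the diet with high-potassium produce in weeks 3 and 4.
- **Schedule (Table 4).** The row "Blood Pressure (systolic and diastolic blood pressure" and the row for the 13-analyte panel are marked at baseline, week 2 and week 4 only. Potassium and the gastrointestinal questionnaire also have a week 1 value.
- **Contrast (section 8).** "For all parameters, baseline values will be compared to values at the end of each diet phase (weeks 2 and 4".
- **Target.** Aim (b) in section 4 is to "evaluate the impact of a plant-rich diet on health outcomes in CKD patients". Section 8 lists, beside the efficacy of patiromer, "as well as the effects of this diet on health outcomes". The same section also speaks more generally of evaluating the interventions, so the wording is mixed.
- **Analysis (section 11.a).** Repeated-measures ANOVA with Tukey HSD. The plan examines changes in "covariates (weight, medications, dose of Patiromer) between baseline and the end of each diet phase" and their relationship to outcome changes. Covariates are reported and not modelled.
- **Magnesium (section 12).** Hypomagnesemia is listed at 5.3% among 734 patients treated with patiromer, and the plant-rich diet is expected to attenuate it. Magnesium is tested at the end of phases I and II.

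**The concern.** Between the baseline and week 2 measurements two things change: the drug starts and the diet changes. No value of these 15 outcomes (systolic pressure, diastolic pressure and 13 analytes) is taken between the two. A change caused by starting patiromer could be reported as a health effect of the plant-rich diet, or an opposing drug effect could hide a diet effect. Magnesium is the concrete case: the documents expect drug and diet to act in opposite directions, and the first on-drug value comes after the diet has begun. What is at stake is the interpretation of aim (b), which is secondary.

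**Working it through.** The plan gives no alpha, power, SD or effect size for these outcomes, so there is no planned figure to reproduce. I take the baseline visit to precede the first dose; the column order of Table 4 implies this, but the text does not state it.

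**1. What the visits can separate.** Let D be the effect of starting the drug, A the phase I diet versus usual diet, B the added high-potassium produce, and T a linear trend per week. Expected changes from baseline:

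- week 1: D + T (not measured for these outcomes)
- week 2: D + A + 2T
- week 4: D + A + B + 4T

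With T = 0, the planned visits give rank 2 for three unknowns: only B and the sums D + A and D + A + B are estimable. Adding week 1 gives rank 3 of 3, so D, A and B separate.

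With T unknown, the combination (D, A, B, T) = (−1, −1, −2, 1) gives zero at every visit: week 1, −1 + 1; week 2, −1 − 1 + 2; week 4, −1 − 1 − 2 + 4. So none of D, A, B or A + B is estimable with or without week 1. A week 1 reference then removes only D and one week of trend, leaving A + T at week 2 and A + B + 3T at week 4.

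**2. Number of contrasts.** 15 outcomes × 2 = 30 baseline contrasts contain D. This describes the structure; it does not show that D differs from zero.

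**3. Illustration of size.** Assumptions: A = B = 0, no trend, sphericity, 10 completers, 5% level, and D in units of the within-person residual SD. Tukey critical values on the t scale are q(3, 18 df)/√2 = 3.61/√2 = 2.55 for three visits and q(4, 27 df)/√2 = 3.87/√2 = 2.74 for four. The smallest significant differences are 3.61/√10 = 1.14 and 3.87/√10 = 1.22 residual SD. Simulated chance (200,000 trials) that at least one of the two contrasts read as diet effects is significant:

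| D (assumed) | Baseline reference | Week 1 reference, D complete by week 1 | Week 1 reference, half of D by week 1 |
|---|---|---|---|
| 0.25 | 7% | 2% | 2% |
| 0.5 | 16% | 2% | 4% |
| 1 | 55% | 2% | 11% |
| 1.5 | 89% | 2% | 26% |

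**4. Week 2 to week 4.** This pair cancels D only if the drug effect is complete by week 2. If half were present then (assumed), a pure drug effect of 0.5, 1 or 1.5 SD would make this pair significant in about 4%, 10% or 22% of trials.

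**5. Magnesium.** At 5.3%, 10 participants give 10 × 0.053 = 0.53 expected cases of hypomagnesemia. No schedule can show attenuation of its incidence at this size; only the mean concentration is informative.

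**The case against.** The strongest reply is that this is a declared quasi-experimental proof of concept in 10 people. Section 2 plans a next trial with an arm on "or a plant-rich diet plus patiomer", so the combined change is what that trial needs. This stands: the combined contrast is legitimate if it is labelled so. The reply does not cover attribution to the diet, which sections 4 and 8 still name as the target.

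It is also fair that the size is assumed. Beyond magnesium the documents link none of the 15 outcomes to patiromer, and a small drug shift (0.25 SD) does little harm. Reporting dose and relating it to outcome changes is useful, but everyone starts the drug before the diet, so it cannot separate drug start from phase I.

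Four stronger readings are tempting and not supported:

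- *Section 15 presents the contrast as a diet result.* Its phrase "the potential health benefits of a plant-rich dietary pattern" concerns knowledge that may benefit future patients and reports no contrast.
- *The default timing sentence in 9.b, with weeks 1 and 3, governs these outcomes and supplies a week 1 value.* That sentence yields to more specific text and points to Table 4 in the same section, which times these outcomes at weeks 2 and 4. Its phase labels agree with Table 4; only the week numbers differ.
- *Week 2 to week 4 is a clean diet effect.* Dose may change at the weekly visits, drug onset and phase I diet effects may be incomplete at week 2, and a trend cannot be excluded.
- *A week 1 value would identify the diet effect.* It would do so only without a time trend, with the drug effect complete by week 1 and with a stable dose.

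**Conclusion.** The point holds for blood pressure and the biochemistry panel. As planned, their changes from baseline measure patiromer plus diet and cannot be credited to the diet alone. That structural conclusion needs only the schedule. The 7% to 89% range rests on assumed drug effects and the conditions listed with it, and is not a forecast. The primary comparison of potassium with pre-treatment screening is not affected. The plan should be changed, mainly in how aim (b) is worded and reported.

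**What to change.** 1. **Label the contrasts (sections 8 and 11).** Call baseline to week 2 and baseline to week 4 changes in health outcomes combined patiromer-plus-diet changes. Describe week 2 to week 4 as the change when high-potassium produce is added on background patiromer, with its limits stated: possible dose change between visits, incomplete drug onset or phase I diet effect at week 2, and time trend. Cost: wording.
2. **Gastrointestinal symptoms.** Use the week 1 value already collected as the reference for changes on diet, with the same kind of limits. Cost: wording.
3. **Optional: measure blood pressure and the panel (at least magnesium) at the existing week 1 fasting visit.** Report baseline to week 1 as the change on patiromer alone, and later changes from week 1 beside the dose report.
   - Blood per participant rises from 5 × 0.5 + 3 × 5.0 = 17.5 mL to 5 × 0.5 + 4 × 5.0 = 22.5 mL. There are 10 more panels (30 to 40) and one more blood pressure measurement per participant.
   - The Tukey critical value rises from 2.55 to 2.74. Power for a true diet change of 1 residual SD, with no drug effect, falls from about 55% to 47% for at least one of two contrasts, and from about 40% to 33% for a single contrast.
   - Pairwise comparisons rise from 15 × 3 = 45 to 15 × 6 = 90. Tukey holds 5% per outcome (15 × 0.05 = 0.75 outcomes expected with a false positive) only under sphericity. With serial correlation of 0.8 per week (assumed) the rate is about 5.6% with three visits and 6.7% with four, or 0.84 and 1.0 outcomes.
4. **Reconcile the text.** Align the week numbers in the 9.b default sentence (1 and 3) with section 8, the baseline-measurement and potassium paragraphs of 9.b, and Table 4 (2 and 4). As a separate consistency point, section 12 promises the gastrointestinal questionnaire every week, whereas 9.b.v and Table 4 omit week 3. Cost: wording, with no added test if both are settled in favour of Table 4.

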iii. Serum potassium concentrations. The primary purpose of this study is to evaluate the efficacy of patiromer for maintaining serum potassium concentrations in CKD patients during transition to a liberalized plant-rich diet by comparing fasting serum potassium concentrations at screening to values at the end of phase I (week 2) and phase II (week 4) of the study. However, because potassium concentrations are also being used to titrate the dose of patiromer needed to achieve normal potassium concentrations, fasting serum potassium concentrations will also be measured at the end of weeks 1 and 3. To ensure a rapid response to changes in serum potassium concentrations, blood samples obtained at the CTSI CRC will be immediately delivered to the study laboratory at Tisch Hospital for analysis, and the results sent to the CTSI Pharmacy for evaluation (section 10.a.i.). Participants will be directed to pick up new prescriptions from the CTSI Pharmacy on the days of measurement. To obtain a measurement of serum potassium concentration, a 0.5 mL sample of blood is required.

iv. Blood pressure. Systolic and diastolic blood pressures will be measured after 5-minutes of rest in a seated position with their arm supported at the level of their heart and their feet resting on the floor using an automatic sphygmomanometer. Blood pressure measurements will be obtained in duplicate with a third measure obtained if the systolic or diastolic values on repeated measurement differ by more than 5 mmHg.

v. Gastrointestinal symptoms. The frequency and severity of participant gastrointestinal symptoms in the previous week (abdominal cramping, abdominal discomfort, indigestion, infrequent or difficult to pass bowel movements, flatulence, loose or watery stools) will be self-reported via an investigator-developed questionnaire at baseline, and at the end of the stabilization period (week 1), phase I diet (week 2), and phase II diet (week 4).

vi. Other biochemical parameters. Fasting blood samples will be obtained at the CTSI CRC, and analyzed for concentrations of phosphorus, calcium, magnesium, albumin, glucose, insulin, cholesterol, LDL-cholesterol, HDL-cholesterol, triglycerides, urea nitrogen, bicarbonate and C-reactive protein. Similar to serum potassium concentrations, blood samples will be delivered by study staff to the laboratory at Tisch Hospital for analysis. To obtain these biochemical measurements, approximately 5.0 mL of blood is required.

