Another intervention feature to lower the risk of hyperkalemia is the close monitoring of participants’ serum potassium concentrations to adjust the dose of patiomer (10.a.i. Table 2). We will measure serum potassium concentrations as per current patiomer recommendations (weekly), and samples will be processed through the Tisch Laboratory, and the results sent to the CTSI Pharmacy for review. If values are abnormally high or rapidly increasing towards hyperkalemia (10.a.i. Table 2), the study nephrologist ([name]) will be immediately contacted. Because hemolysis can cause artificially elevated serum potassium values, participants with abnormally high or rapidly increasing concentrations of serum potassium will have another blood test to confirm their serum potassium concentrations.

In addition to risks associated with hyperkalemia, there are potential risks related with patiromer use. In a sample of 734 patients treated with patiromer, the most common AEs were constipation (7.2%), hypomagnesemia (5.3%), diarrhea (4.8%), nausea (4.8%), abdominal discomfort (2.0%) and flatulence (2.0%). It is likely that the most common of these AEs (constipation, hypomagnesemia, diarrhea) would be attenuated by a plant-rich diet, which contains higher amounts of fiber and magnesium compared to the typical Western diet. The less common adverse events (abdominal discomfort, flatulence) may be exacerbated by the higher intakes of dietary fiber. These potential AEs will be assessed at the end of each week through the gastrointestinal symptoms questionnaire, and blood testing at the end of phase I and II (for hypomagnesemia). Patiromer also has the potential to bind to other medication, reducing their absorption. This will be mitigated by directing patients to take patiromer once daily, and at least 3 hours away from other medications.

It is unlikely that women and men with stages 3-4 CKD will become pregnant or impregnate someone. Additionally, we will exclude anyone who is planning on becoming pregnant from the study. As part of our Clinical Trial Agreement with Relypsa, Inc., we will report any pregnancies (whether female or male impregnating a female) to Relypsa, Inc. In addition, because the patiromer and the research diets are untested in pregnant women, we will withdraw women who become pregnant during the study period.

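### Gastrointestinal symptoms are compared only with the pre-patiromer baseline, so the planned diet contrast estimates patiromer plus diet, although a patiromer-only week 1 questionnaire is already scheduled

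*Combined protocol and SAP*

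**What the plan says.** - **Aim.** Section 4 gives one focus of the study as to "evaluate the impact of a plant-rich diet on health outcomes in CKD patients". Section 8 lists gastrointestinal symptoms among those outcomes.
- **Sequence.** Section 9.a (Design) begins the feeding study as follows: "After a 1-week stabilization period, in which participants are prescribed Patiromer while following their usual diets". The low-potassium plant-rich diet occupies week 2 and the liberalized diet weeks 3 and 4.
- **Measurement.** Section 9.b.v schedules the gastrointestinal questionnaire at baseline "and at the end of the stabilization period (week 1), phase I diet (week 2), and phase II diet (week 4"). Table 4 agrees. Blood pressure and the wider blood panel have no week 1 measurement.
- **Comparison.** Section 8 says: "For all parameters, baseline values will be compared to values at the end of each diet phase (weeks 2 and 4"). Section 11 examines changes "between baseline and the end of each diet phase" and has gastrointestinal symptoms in its outcome list. The method is repeated-measures ANOVA with Tukey HSD; the visits entered are not listed.
- **Expected effects.** Section 12 reports that in 734 patients on patiromer "the most common AEs were constipation (7.2%), hypomagnesemia (5.3%), diarrhea (4.8%), nausea (4.8%), abdominal discomfort (2.0%) and flatulence (2.0"%). It expects the diet to attenuate constipation and diarrhea, and adds: "The less common adverse events (abdominal discomfort, flatulence) may be exacerbated by the higher intakes of dietary fiber".

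**The concern.** The reference visit does not match the question. Between baseline and week 2 two things change: patiromer is started, then the diet is changed. A difference between these visits carries both effects, yet the stated aim concerns the diet.

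This matters more for gastrointestinal symptoms than for most of the other outcomes, because section 12 expects drug and diet to act on the same symptoms. For constipation and diarrhea it expects them to act in opposite directions, so a baseline contrast could hide an attenuation by the diet. For discomfort and flatulence they may act in the same direction, so symptoms caused by the drug could be read as caused by the diet. The follow-on trial described in section 2 would inherit whichever reading is reported.

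Gastrointestinal symptoms are also the only health outcome, apart from potassium, with a measurement at the end of the patiromer-only week. A partial remedy therefore needs no new data.

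**Working it through.** The plan gives no power, effect size, SD or item scale for this outcome, so there is no figure of its own to reproduce. The check is structural, followed by illustrations of size.

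**1. What each contrast estimates.** For one symptom score, let P be the shift from baseline to week 1 (patiromer, plus any change with time), C the further change in the drug or time effect from week 1 to a later visit, and D the diet effect at that visit.

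- Baseline to week 1 = P
- Baseline to week 2 or 4 = P + C + D (the planned contrast)
- Week 1 to week 2 or 4 = C + D

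The planned contrast equals D only if P + C = 0. The week 1 contrast equals D only if C = 0. If P is positive, D negative and smaller in size than P, and C = 0, the planned contrast is positive although the diet reduced the symptom. The sign of the prediction in section 12 would be reversed.

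**2. How often a drug-related symptom might be present.** Inputs: n = 10 (section 5) and the section 12 rates. Assumption: the rates apply by week 1 and participants are independent. The chance of at least one affected participant is 1 − (1 − p)^10.

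- Constipation, p = 0.072: 1 − 0.928^10 = 0.53; expected number 10 × 0.072 = 0.72
- Diarrhea, p = 0.048: 1 − 0.952^10 = 0.39; expected number 10 × 0.048 = 0.48

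These are kept apart because section 9.b.v lists the two symptoms as separate items.

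**3. What a drug shift could do to the planned test.** This is a simulation of 20,000 trials with n = 10, independent normal residuals, a true diet effect of 0, C = 0 and Tukey HSD at 0.05. The shift sizes are assumptions; the documents give none. The entries are the proportion of trials in which each contrast is flagged.

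| Assumed P (residual SD) | Baseline to week 2 or 4, three visits | Week 1 to week 2 or 4, four visits |
|---|---|---|
| 0 | about 2% | about 1% |
| 0.5 | about 10% | about 1% |
| 1.0 | about 40% | about 1% |
| 1.5 | about 78% | about 1% |

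The last column is favourable by construction, because C was set to 0.

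**4. Cost of the extra visit.** The Tukey critical difference in residual SD is q/√n.

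- Three visits, 18 error df: 3.609/√10 = 1.14
- Four visits, 27 error df: 3.870/√10 = 1.22

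The pairs per item rise from 3 to 6. If all six symptoms are scored separately for frequency and severity, which the plan does not settle, the named contrasts rise from 6 × 2 × 2 = 24 to 6 × 2 × 5 = 60.

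**The case against.** Five points can be made for the plan.

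1. **Week 1 is not ignored.** A reader might infer that the week 1 questionnaire is collected and never used. The documents do not support that: section 11 promises summaries of outcomes at each time point, and section 12 uses the questionnaire to watch for adverse effects of patiromer. This stands, but neither use puts week 1 into the diet comparison.
2. **Tukey HSD compares all pairs.** If week 1 is entered, the week 1 contrasts follow automatically. But section 11 does not say that it is entered, and the only comparisons named leave it out.
3. **The combined regimen is a legitimate target.** The later trial in section 2 would test a plant-rich diet plus patiromer. This stands, and is a reason to keep the baseline contrasts under a correct label. It does not make them estimates of the diet effect named in section 4.
4. **Week 1 is an imperfect reference.** A reader might infer that switching to week 1 would cleanly separate drug from diet. It would not. Week 1 is a single week at the starting dose, section 9.a.i allows the dose to change from the end of that week, and there is no control group. If a symptom caused by patiromer resolves on its own after week 1 (C = −P), the week 1 contrast shows a false attenuation by the diet while the baseline contrast is correct. A symptom starting after week 1 would still be read as diet. This stands in full.
5. **The size is uncertain.** Section 12 gives no follow-up time for its rates, and section 4 excludes people with bowel disease. A reader might also pool constipation and diarrhea and quote 1 − 0.88^10 = 0.72, but that assumes no overlap and describes no single item. Nor can a shift in the mean score be given, because no item scale is stated.

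**Conclusion.** The point holds in a limited form. For the aim of assessing the diet, the named gastrointestinal contrasts estimate patiromer plus diet, and a scheduled measurement that would remove the week 1 part of the drug effect is not named in the diet comparison. This follows from sections 4, 8, 9 and 11 without any numerical assumption.

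The size is illustrative only: about a 53% chance of at least one affected participant for constipation and 39% for diarrhea, if the section 12 rates apply by week 1. The simulated flag rates depend on assumed shifts and on a drug effect that stays constant after week 1. Nothing in the documents shows that a conclusion would change.

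The consequence is moderate. Gastrointestinal symptoms are not the primary outcome, and this is a proof-of-concept study of 10 people. The baseline contrast is not invalid; it answers the combined-regimen question and needs that label.

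**What to change.** In sections 8 and 11, for gastrointestinal symptoms:

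- State that baseline and weeks 1, 2 and 4 all enter the repeated-measures analysis.
- Name week 1 to week 2 and week 1 to week 4 as the diet-phase contrasts.
- Report baseline to week 1 as the patiromer run-in change.
- Keep baseline to weeks 2 and 4, labelled as the combined patiromer-plus-diet change.
- Show patiromer dose at each visit beside the symptom results.
- State the limits of the week 1 reference given in the objection, so that a fall after week 1 is not reported as proof of a diet effect.

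Reconcile two related passages at the same time. Section 12 describes the questionnaire as weekly, but Table 4 has none at week 3. The opening of section 9.b places the phase ends at weeks 1 and 3, against weeks 2 and 4 elsewhere.

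No visit or questionnaire is added to the Table 4 schedule. The price is more comparisons at n = 10 and a Tukey critical difference of 1.22 instead of 1.14 residual SD. Tukey HSD controls error within one item but not across items, so the results should be presented as exploratory.
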